6.2.1 Background Glucose-Lowering Medications

Eligible participants must be on one to four non-insulin glucose-lowering medication(s) without a severe hypoglycemic event within the past six months of the screening visit.

Participant's background medication will be kept stable (no change in medication or dose) for at least 12 weeks prior to the Baseline Visit.

Peri-procedurally, the dose of medications with hypoglycemic risks will be adjusted per guidelines provided in **Section 6.2.2**.

During the transitional diet period, participant's medication will be titrated to the background level and maintained stable until the Week 24 Visit has been completed. Medication and/or dose change necessary for managing hypoglycemia, hyperglycemia, or other safety concerns is permitted. Reason for the medication change must be documented on eCRF.

Following the Week 24 Visit, participants will be managed according to the current (2020) guidelines of the American Diabetes Association² and their glucose-lowering medications will be optimized as necessary to reach an HbA1c target of 7%.

Background medications are non-investigational products. They should be used in accordance with standard of care and their approved labeling. They will not be provided by the sponsor except if required by local regulations.

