7.12.5 Unscheduled Visits

If a participant is hospitalized, seen in the emergency room, or has an unscheduled clinic visit, efforts should be made to collect the following data:

- Relevant medical history, physical examination, and laboratory test findings
- Concomitant medications
- Assessment of AEs

These assessments should be documented on the eCRFs as appropriate.

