4.2.1. Secondary Endpoints

First Secondary Endpoint: Procedure success: defined as successful treatment of at least 6 cm of duodenum segment.

Second Secondary Endpoint: Procedure time: defined as the time between the Endogenex catheter insertion and the catheter removal.

Third Secondary Endpoint: Change from baseline (post-baseline minus baseline) in HbA1c reported for each pre-specified study visit.

Note: The estimates will be derived using a mixed model repeated measure procedure; the 24 week result will be the principal time point of interest.

Fourth Secondary Endpoint: Change from baseline (post-baseline minus baseline) in Fasting plasma glucose (FPG) reported for each pre-specified study visit.

Note: The estimates will be derived using a mixed model repeated measure procedure; the 24 week result will be the principal time point of interest.

Fifth Secondary Endpoint: Change from baseline (post-baseline minus baseline) in Insulin-resistance by HOMA-IR reported for each pre-specified study visit.

Note: The estimates will be derived using a mixed model repeated measure procedure; the 24 week result will be the principal time point of interest.

Sixth Secondary Endpoint Part 6a: Change from baseline (post-baseline minus baseline) in Post-prandial plasma glucose (PPG) based on mixed meal tolerance test (MMTT) reported for each pre-specified study visit.

Note: The estimates will be derived using a mixed model repeated measure procedure; the 12 week result will be the principal time point of interest.

Sixth Secondary Endpoint Part 6b: Change from baseline (post-baseline minus baseline) in beta cell function based on mixed meal tolerance test (MMTT) reported for each pre-specified study visit.

Note: The estimates will be derived using a mixed model repeated measure procedure; the 12 week result will be the principal time point of interest.

Sixth Secondary Endpoint Part 6c: Change from baseline (post-baseline minus baseline) in the disposition index based on mixed meal tolerance test (MMTT) reported for each pre-specified study visit.

Note: The estimates will be derived using a mixed model repeated measure procedure; the 12 week result will be the principal time point of interest.

Seventh Secondary Endpoint: o Time in range, glucose variability by continuous glucose monitoring (CGM)

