The *Level 3* display will be used for summarizing the parameters recorded multiple times during the follow-up visits. An example of the layout is presented below; rows will be repeated for all visits where a measurement is recorded using the expanded time windows.

Level 3a Display

Parameter and Statistic	Observation Time	Device Generation 1 / 600 Volts / Single Treatment	Device Generation 1 / 600 Volts / Double Treatment	Device Generation 2 / 750 Volts / Double Treatment	All Patients
HbA1c	Baseline				
HbA1c	Post-Procedure Visit xxx				
HbA1c	Change from Baseline				

Level 3b Display

Parameter and Statistic	Observation Time	Device Generation 1 / 600 Volts / Single Treatment	Device Generation 1 / 600 Volts / Double Treatment and Device Generation 2 / 750 Volts / Double Treatment	All Patients
HbA1c	Baseline			
HbA1c	Post-Procedure Visit xxx			
HbA1c	Change from Baseline			

There will be 2 sets of comparative analyses prepared, each predicated on different combinations of device generation, voltage, and single vs. double treatment. The planned comparisons are outlined below.

Comparison Set 1

Device Generation 1 / 600 Volts / Single Treatment vs.

Device Generation 1 / 600 Volts / Double Treatment vs.

Device Generation 2 / 750 Volts / Double Treatment

Comparison Set 2

Device Generation 1 / 600 Volts / Single Treatment vs.

Device Generation 1 / 600 Volts / Double Treatment plus Device Generation 2 / 750 Volts / Double Treatment

Supportive individual patient data Listings will be sorted and presented by site number, patient number and visit date, if applicable. Listings will also include the number of days relative to the DMR index procedure. Specific algorithms are discussed for imputing missing or partially missing data, if deemed appropriate, under specific data topics. Imputed or derived data will be flagged in the individual patient data Listings. Imputed data, restricted to dates, will not be incorporated into any raw or primary datasets from the electronic capture system. The imputed data will be retained in the derived / analysis datasets.

Summary statistics will consist of the number and percentage of responses or counts at each level for categorical variables (e.g. race). For continuous variables, and the sample size (n), mean, median, standard deviation (SD), minimum, and maximum values will be presented.

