8.6. Unscheduled Visit Information

Information for this presentation of the recorded data will come from the individual datasets where the visit name is listed as *Unscheduled*. Listing 16.4.9 entitled *Unscheduled Visit Information* will be sorted by site number, and patient.

The table below provides the specification for assignment of an unscheduled visit. If there are multiple records within an interval, date of the latest record will be used.

Visit Name	Clinic (Visit) / (R)emote Visit	Timing of the Visit (weeks)	Protocol Visit Window			Expanded Visit Window		
			Protocol Visit Window (days)	First Interval Day	Last Interval Day	First Interval Day	Last Interval Day	Expanded Visit Window (days)
Screening	R1	-12	-84 to -5	-84	-5			
Baseline[1]	V2	-3	-28 to -1	-28	-1			
Index Procedure	V3	0						
Week 1	R4	1	±2	5	9	5	9	2
Week 2	R5	2	±3	11	17	10	18	4
Week 4	V6	4	±5	23	33	19	37	9
Week 8	R7	8	±7	49	63	38	74	18
Week 12	R8	12	±7	77	91	73	95	11
Week 16	R9	16	±7	105	119	96	128	16
Week 20	R10	20	±7	133	147	129	151	11
Week 24	V11	24	±7	161	175	152	184	16
Week 28	R12	28	±7	189	203	185	207	11
Week 32	R13	32	±7	217	231	208	240	16
Week 36	V14	36	±7	245	259	241	263	11
Week 40	R15	40	±17	273	287	264	296	16
Week 44	R16	44	±7	301	315	295	321	13
Week 48 (End of Study)	V17	48	30	306	366	322	366	14

Visit Name	Clinic (Visit) / (R)emote Visit	Timing of the Visit (weeks)	Target Visit Day	Number of Days on Either Side of the Target Day to define the Expanded Time Window
Screening	R1	-12		
Baseline[1]	V2	-3		
Index Procedure	V3	0		
Week 1	R4	1	7	2
Week 2	R5	2	14	4
Week 4	V6	4	28	9
Week 8	R7	8	56	18
Week 12	R8	12	84	11
Week 16	R9	16	112	16
Week 20	R10	20	140	11
Week 24	V11	24	168	16
Week 28	R12	28	196	11
Week 32	R13	32	224	16
Week 36	V14	36	252	11
Week 40	R15	40	280	16
Week 44	R16	44	308	13
Week 48 (End of Study)	V17	48	336	14

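### SAP 8.6 takes the latest record in a visit interval without giving the scheduled visit priority, so a result taken after the Week 24 drug hold ends could replace the scheduled Week 24 value

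*SAP*

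**What the plan says.** SAP 8.6 introduces its table of windows with "The table below provides the specification for assignment of an unscheduled visit" and follows it with "If there are multiple records within an interval, date of the latest record will be used". The Week 24 row reads "Week 24 V11 24 ±7 161 175 152 184 16", that is, a protocol window of days 161 to 175 and an expanded window of days 152 to 184. The companion table gives "Week 24 V11 24 168 16": target day 168, with 16 days either side.

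SAP Section 7 carries these windows into the results. For the Level 3 layout, whose example parameter is HbA1c, it says that "rows will be repeated for all visits where a measurement is recorded using the expanded time windows".

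SAP 4.2.1 says of HbA1c, FPG and HOMA-IR in turn that "the 24 week result will be the principal time point of interest". The eighth secondary endpoint is HbA1c response at 24 weeks. The ninth asks whether that response is kept at 48 weeks and leaves out patients who did not respond at 24 weeks, so the Week 24 value also sets its denominator.

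SAP 5.1 holds background drugs stable up to the 24-week visit and has them optimised towards an individual A1c goal afterwards. Protocol 6.2.1 does the same: after the visit, "their glucose-lowering medications will be optimized as necessary to reach an HbA1c target of 7" percent. Protocol 7.12.5 asks sites to try to collect relevant laboratory findings "If a participant is hospitalized, seen in the emergency room, or has an unscheduled clinic visit", and SAP 8.5 includes unscheduled laboratory tests in the laboratory listing.

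Nothing in either document gives priority to the scheduled record, to the record closest to target, or to a record taken before a drug change.

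**The concern.** Week 24 is the last scheduled measurement before background drugs may be optimised, which is why it is the natural point at which to read the effect of the procedure. The expanded window stays open for days after that visit. Under a latest-record rule, an unscheduled result can displace the scheduled one only if it was taken later. At Week 24, later means after the drug hold has ended. A displaced value would therefore mix the effect of the procedure with whatever was changed after the visit, or with the illness that prompted the extra test.

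Unscheduled results come from events and not from a calendar, so the patients affected would not be a random subset. The quantities at stake are the Week 24 means for HbA1c, FPG and HOMA-IR and the two HbA1c responder endpoints, reported in groups as small as 3 and 7.

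**Working it through.** **Window.** Target day ± half-width: 168 − 16 = 152 and 168 + 16 = 184. This reproduces the Week 24 row exactly. The Week 28 expanded window opens on day 185, so any result up to day 184 belongs to Week 24.

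**Could a scheduled test cause the problem?** No. SAP Section 9 lists HbA1c, FPG and HOMA-IR at Weeks 4, 12, 24, 36 and 48. A second glycaemic record in the Week 24 interval after the visit has to be unscheduled.

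**Exposure.** Days after the scheduled visit that still fall in the interval = 184 − visit day.

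| Scheduled Week 24 visit | Days left in the interval |
|---|---|
| Day 161 (first day of protocol window) | 184 − 161 = 23 |
| Day 168 (target) | 184 − 168 = 16 |
| Day 175 (last day of protocol window) | 184 − 175 = 9 |

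A visit on day 152, the first day of the expanded window, would leave 32 days.

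**Effect on a mean.** Shift = k × d / N, where k is the number of replaced records and d is the change in value for each, all in the same direction. The documents give neither k nor d, so both are assumed. N is 20 in total, in groups of 3, 7 and 10 (SAP Section 3). The formula is for the observed mean; with nearly complete data, the mixed model's Week 24 estimate would move by about as much.

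- HbA1c, N = 20: lowest 1 × 0.1 / 20 = 0.005 points; highest 3 × 0.5 / 20 = 0.075 points.
- HbA1c, one record with d = 0.5: 0.05 points (N = 10), 0.07 (N = 7), 0.17 (N = 3).
- FPG, N = 20: lowest 1 × 1 / 20 = 0.05 mmol/L; highest 3 × 2 / 20 = 0.30 mmol/L.
- FPG, one record with d = 1 to 2 mmol/L: 0.10 to 0.20 mmol/L (N = 10), 0.14 to 0.29 (N = 7), 0.33 to 0.67 (N = 3).

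**Effect on a proportion.** One changed responder moves it by 100 / N: 5 percentage points at N = 20, and 10, 14.3 or 33.3 points in the groups of 10, 7 and 3. This assumes that the responder endpoints use the same Week 24 HbA1c as the Level 3 tables. SAP 9.2 puts them in Level 1 tables, for which the window is not restated. For the ninth endpoint the denominator is smaller still, because 24-week non-responders are left out.

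**Does the Per-Protocol analysis remove it?** Not reliably. SAP Section 6 requires stable drugs for 24 weeks only. A change after a visit on day 168 or later does not by itself exclude the patient. Read literally, a change on days 161 to 167 would.

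**The case against.** The strongest reply concerns scope. The sentence sits in the section on unscheduled visits, which supports a listing of those visits, and it speaks of the date of the latest record. It can be read as choosing only among several unscheduled records, with scheduled values untouched. Section 7 applies the windows to the Level 3 tables but does not repeat the latest-record rule. That reading is open and cannot be excluded. It leaves a different gap, though: the SAP would then have no rule for an interval that holds both a scheduled and an unscheduled result. The same sentence is needed either way.

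Second, the trigger is narrow. It takes an unscheduled HbA1c, FPG or insulin result within a few weeks, and Protocol 7.12.5 does not call for those tests specifically. The SAP also names a different study document (REGENT-1-US, Doc. No. 346) from the protocol supplied, so that protocol section may not govern. This limits what can be said about frequency. It does not touch the rule, the windows, the end of the drug hold or the principal time point, which are all in the SAP.

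Third, these are secondary endpoints in a feasibility study without formal hypothesis tests, and all data are listed, so a substitution could be traced. That bears on the weight of the point. The estimates are still the study's output, and SAP Section 3 foresees their use in regulatory submissions and manuscripts.

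A reader might also infer that the rule systematically prefers contaminated values or flatters the device. The documents do not support that. An unscheduled result taken before the scheduled visit, from day 152 on, leaves the scheduled value in place. Optimisation is done only as necessary, so not every later value is on changed drugs. Optimised drugs would tend to lower glucose, while acute illness could raise it. Nor is every scheduled Week 24 value on unchanged drugs, since Protocol 6.2.1 permits earlier changes for safety.

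**Conclusion.** The SAP leaves open, and on one plain reading directs, that an unscheduled result taken after the Week 24 drug hold has ended replaces the scheduled value at the principal time point for HbA1c, FPG and HOMA-IR. The window for this is 16 days after an on-target visit and 9 to 23 days across the protocol window.

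This is a possible bias of unknown frequency and direction, not a demonstrated one. Under the assumed shifts, the effect on the overall HbA1c mean is small. The groups of 3 and 7 and the responder proportions are more exposed. The conclusion rests on reading the latest-record sentence together with the Level 3 statement in Section 7. On the narrower reading, what remains is a missing precedence rule. The point is worth correcting because doing so costs almost nothing and removes a choice that would otherwise be made with the data in hand.

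**What to change.** State three things in SAP 8.6:

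- The scheduled visit's value is used whenever it exists.
- If it is missing, the unscheduled record closest to the target day within the expanded window is used.
- For Week 24 analyses, an unscheduled value is not used if it was taken after a glucose-lowering drug change made under the post-Week-24 optimisation.

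Closest to target is one reasonable fallback; what matters is that the order is fixed before database lock. With this rule, the number of days on which a later result can replace an existing scheduled Week 24 value falls from 9 to 23 (protocol-window visits) to 0.

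The cost is one or two sentences in the SAP, a small programming change, and possibly a few more missing Week 24 values. Patient care is unaffected.

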8.7. Vital Signs Recorded Over the Course of the Study

Vital signs will include blood pressure and heart rate and be presented using the Level 3 table format. Data will be summarized and reported in Table 14.1.7 entitled *Summary of the Vital Sign Results* (ITT population) using the Level 3 table design; Table 14.1.7a will be restricted to the FAS population. Listing 16.4.10 entitled *Vital Sign Results* provides supportive data for Tables 14.1.7 and 14.1.7a and will be sorted by site number, and patient number.

9. ENDPOINTS ANALYSES

There is a single primary endpoint and 18 secondary endpoints. Based on the feasibility nature of this study, there are no formal hypothesis tests.

Primary Endpoint

The primary endpoint of the study is predicated on safety; the distribution of this endpoint is binary. The primary population for analysis of this endpoint will be the ITT population.

Proportion of patients experiencing one or more device- or procedure-related serious adverse events at 12 weeks post-procedure.

All device-related or procedure-related serious adverse events from the start of the study procedure through relative study day 84 will be used in the tabulation.

The secondary endpoints are listed below:

First Secondary Endpoint

The distribution of this endpoint is binary. The primary population for analysis of this endpoint will be the FAS population.

Procedure success: defined as successful treatment of at least 6 cm of duodenum segment.

Immediately following the study procedure, a determination will be made regarding treatment of ≥ 6 cm of the duodenum. Patients who fail to have ≥ 6 cm of the duodenum treated, for any reason, will be counted as not having achieved **Procedure Success**.

Second Secondary Endpoint

The distribution of this endpoint is continuous. The primary population for analysis of this endpoint will be the FAS population.

Procedure time: defined as the time between the Endogenex catheter insertion and the catheter removal.

Procedure Time will be reported in minutes.

Third Secondary Endpoint

The distribution of this endpoint is continuous. The primary population for analysis of this endpoint will be the FAS population.

Change from baseline (post-baseline minus baseline) in HbA1c reported for each pre-specified study visit.

The pre-specified study visits where HbA1c is recorded is Week 4, 12, 24, 36, 48.

Fourth Secondary Endpoint

The distribution of this endpoint is continuous. The primary population for analysis of this endpoint will be the FAS population.

Change from baseline (post-baseline minus baseline) in Fasting plasma glucose (FPG) reported for each pre-specified study visit.

The pre-specified study visits where FPG is recorded is Week 4, 12, 24, 36, 48.

Fifth Secondary Endpoint

The distribution of this endpoint is continuous. The primary population for analysis of this endpoint will be the FAS population.

Change from baseline (post-baseline minus baseline) in Insulin-resistance by HOMA-IR reported for each pre-specified study visit.

The pre-specified study visits where HOMA-IR is recorded is Week 4, 12, 24, 36, 48.

Sixth Secondary Endpoint 6a

The distribution of this endpoint is continuous. The primary population for analysis of this endpoint will be the FAS population. The estimates will be derived using a mixed model repeated measure procedure; the 12 week result will be the principal time point of interest.

Change from baseline in glycemic parameters [Post prandial plasma glucose (PPG) by mixed meal tolerance test (MMTT)] post index procedure, by visit

Sixth Secondary Endpoint 6b

The distribution of this endpoint is continuous. The primary population for analysis of this endpoint will be the FAS population. The estimates will be derived using a mixed model repeated measure procedure; the 12 week result will be the principal time point of interest.

Change from baseline in glycemic parameters [Beta cell function by mixed meal tolerance test (MMTT)] post index procedure, by visit

Sixth Secondary Endpoint 6c

The distribution of this endpoint is continuous. The primary population for analysis of this endpoint will be the FAS population. The estimates will be derived using a mixed model repeated measure procedure; the 12 week result will be the principal time point of interest.

Change from baseline in glycemic parameters [Disposition Index (DI) by mixed meal tolerance test (MMTT)] post index procedure, by visit

The pre-specified study visits where PPG is recorded is Week 4, 12, 24, 36, 48.

Seventh Secondary Endpoint

The distribution of this endpoint is continuous. The primary population for analysis of this endpoint will be the FAS population. The estimates will be derived using a mixed model repeated measure procedure; the 12 week result will be the principal time point of interest.

Time in range, glucose variability by continuous glucose monitoring (CGM)

Eighth Secondary Endpoint

The distribution of this endpoint is binary. The analysis will be based on the proportion of patients that meet the endpoint at 24 weeks post-procedure. The primary population for analysis of this endpoint will be the FAS population.

Proportion of treated patients with an HbA1c improvement of $\geq 0.5\%$ from baseline at 24 weeks (24 week score minus baseline score). Patients who fail to have HbA1c improvement of ≥ 0.5 points from baseline, for any reason, will be counted as not having achieved this endpoint.

Ninth Secondary Endpoint

The distribution of this endpoint is binary. Proportion of treated patients who achieve a HbA1c improvement of $\geq 0.5\%$ or more at 24 weeks from baseline and maintained at 48 weeks. Patients who fail to maintain HbA1c improvement $\geq 0.3\%$ at 48 weeks, for any reason, will be counted as not having achieved this endpoint. Patients who fail to achieve a HbA1c $\geq 0.5\%$ at 24 weeks will be excluded from the tabulation. The primary population for analysis of this endpoint will be the FAS population.

Proportion of treated patients with an HbA1c improvement $\geq 0.5\%$ from baseline at 24 weeks maintained at 48 weeks.

Tenth Secondary Endpoint: The distribution of this endpoint is continuous. The primary population for analysis of this endpoint will be the FAS population. Change in weight from baseline (post-baseline minus baseline) by visit. Weight change will be reported in both kilograms and %TBWL.

Eleventh Secondary Endpoint: Change in glucose-lowering medication usage.

Twelfth Secondary Endpoint: The distribution of this endpoint is continuous. The primary population for analysis of this endpoint will be the FAS population. Change in liver enzyme from baseline at 24 weeks (post-baseline minus baseline) for Alanine Aminotransferase (ALT).

Thirteenth Secondary Endpoint: The distribution of this endpoint is continuous. The primary population for analysis of this endpoint will be the FAS population. Change in liver enzyme from baseline at 24 weeks (post-baseline minus baseline) for Aspartate Aminotransferase (AST).

Fourteenth Secondary Endpoint: The distribution of this endpoint is continuous. The primary population for analysis of this endpoint will be the FAS population. Change from baseline in blood pressure by visit (systolic and diastolic run separately).

Fifteenth Secondary Endpoint: The distribution of this endpoint is continuous. The primary population for analysis of this endpoint will be the FAS population. Change in lipid profile from baseline by visit: total cholesterol

Sixteenth Secondary Endpoint: The distribution of this endpoint is continuous. The primary population for analysis of this endpoint will be the FAS population. Change in lipid profile from baseline by visit: triglycerides

Seventeenth Secondary Endpoint: The distribution of this endpoint is continuous. The primary population for analysis of this endpoint will be the FAS population. Change in lipid profile from baseline by visit: HDL

Eighteenth Secondary Endpoint: The distribution of this endpoint is continuous. The primary population for analysis of this endpoint will be the FAS population. Change in lipid profile from baseline by visit: LDL

